13.0 Withdrawal of Subjects*

- 13.1* The person in charge of the research study or the sponsor can remove you from the research study without your approval. Possible reasons for removal include: Will release from prison after recruitment for study participation ends, lost eligibility to be a research participant; or interfered with ability to complete study protocol.
- 13.2* If a subject is to be withdrawn, an IRB approved withdrawal letter with the reason for withdrawal is sent to the participant. Subject withdrawals are tracked and reported to the IRB.
- 13.3* If a subject is withdrawn from the study by the research team for one of the reasons listed here, the research team will use information collected during the interviews to help determine whether the TARGET model is effective in helping people released from prison. Participants are informed of this protocol during the informed consent process.

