5.0 Procedures Involved*

6.1 The proposed 5-year study is a two-armed 1:1 Randomized Controlled Trial (RCT) implementing and evaluating the effectiveness of a comprehensive trauma-based reentry program for young men releasing from prison to the community evaluated as moderate- to high- risk for recidivism. A total of 400 18-35 year old males releasing to one of the four participating urban and rural counties in Florida (Columbia, Duval, Leon, and Suwanee) will be randomly assigned to participate in the comprehensive trauma-based reentry program or a treatment-as-usual (TAU) control group. Participants in the comprehensive trauma-based reentry program will participate in up to four group sessions while incarcerated and up to 15 group sessions in the community after release. The effectiveness of the comprehensive trauma-based reentry program for 18-35 year old males will be evaluated on the following constructs: key mechanisms of change, community stability, and recidivism. Participants assigned to the treatment-as-usual control group will remain eligible to participate in all reentry services they normally would have received.

The purpose of this study is to evaluate the impact of a comprehensive trauma-based reentry program for moderate- to high-risk young incarcerated males between the ages of 18-35 on post-release outcomes. We will assess changes in key mechanisms of change (i.e. mediators) as well as post-release outcomes. The key mechanisms of change include: trauma symptoms (PTSD, depression, anxiety, and substance abuse), coping, impulsivity, and aggression. Post-release outcomes include community stability (i.e., housing and employment), and recidivism (i.e., re-arrest and re-incarceration for technical violation or new crime; time to re-incarceration).

5.2 Research team members are trained interventionists in order to assess if there are adverse behaviors or thoughts during service delivery (treatment group) and during data collection interviews (all participants). All interviews are conducted one-on-one so the research team member can assess for adverse reaction to the data collection or treatment delivery.

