5.3 Research team members have experience working with people with trauma histories. This is important so they can successfully assess if there are adverse behaviors or thoughts during service delivery (treatment group) and during data collection interviews (all participants). All interviews are conducted one-on-one so the research team member can assess for adverse reaction to the data collection or treatment delivery.

6.4 Data will be collected from participants during one-on-one interviews. Interviews will occur in a private space, where the conversation between the team member and individual cannot be

heard. Data will be recorded in RedCap computer software. Potential participants will complete 12 -count trauma checklist as a screener for assessing for presence of at least one LTE. Eligible participants will plan to release to one of our four Florida counties. Participants will be consented using a Florida State University IRB consent form. If the individual meets screening criteria and consents into the study, the research team member will complete the baseline interview.

All consented participants (treatment and control) will complete a series of interviews. Baseline interviews will occur immediately after consent and occur in prisons. Follow-up interviews will be conducted in the community and timepoints include (1) after the conclusion of the program period, (2) three months after the conclusion of the program period, and (3) nine months after the conclusion of the program period.

6.5 Measures were selected based on the quality of established psychometric evidence and use with criminal justice-involved or other at-risk populations.

- Risk Assessment. Spectrum is the assessment tool used by FDC that identifies risk factors for criminal behavior. Scores on Spectrum range 1-5. The assessment is given to individuals at intake, periodically throughout incarceration and then again under a year before they release and measures an individual's risk to recidivate.
- Trauma screener. A dichotomous Yes/No measure of 12 LTEs from the Trauma Assessment for Adults serves as the trauma screening tool. Participants are identified as eligible if they have experienced at least one LTE.
- Demographics. Age, race/ethnicity, marital status, level of education at release, age at first offense, number of prior incarcerations, most serious offense, and current sentence length will be collected from FDC administrative databases.

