The researcher will conduct consent procedures. The researcher will read aloud the consent form and allow for participants to have time to read the consent form on their own. The researcher will assure participants that their supervision will not be affected by their choice to participate or not participate in the study. The participants will also be told they can discontinue the study at any point or refuse to answer any questions without consequence. The benefits and risks of the study will be reviewed as will the expectations and limitations to breaches of confidentiality. Participants will be provided with two copies of the consent form – one for the participant to sign, either esign or paper signature, and return to the researcher and the other for the participant to keep. However, the participant is not obligated to keep the consent form. The participant is offered a copy to keep so they will have information about how to contact the research team with further questions and the IRB contact information. If participant chooses not to keep the consent form, they will be told that they can always request a consent form after release if they so choose. No aspect of the study will proceed until the consent process is completed. A researcher will inform participants that if they decide not to be in this study, or stop participating at any time, they will not be penalized or lose any benefits for which they otherwise qualify. A researcher will also inform participants that their sentence, program participation, employment opportunities, or any other aspects of their supervision by the DOC will not be affected by their choice to participate. Participants will be informed that their responses will be kept confidential to the fullest extent of the law. If a participant discloses they are the perpetrator or victim of sexual assault within the prison milieu, the incident will be addressed in accordance with PREA guidelines.

- 12.2 Participants receive \$30.00 for completing each of the three post-release interviews. The three follow-up interview timepoints are: (1) after the conclusion of the program period (post-test), (2) three

Commented [A2]: Add e-signature

months after the conclusion of the program period, and (3) nine months after the conclusion of the program period. Research participants will not get money for completing the baseline measurement packet while incarcerated.

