18.0 Provisions to Protect the Privacy Interests of Subjects

18.1 Research participants are not ever required to meet with somebody whom they do not want to interact. If the participant would like a different interviewer, or a different person to facilitate the TARGET sessions if they are in the treatment group, then the research team will grant them that wish if possible. The participant will be informed at consent, and reminded throughout the study, that they can choose to stop any interview or intervention session at any time without any consequences or repercussions whatsoever. The participant has the option to not answer any questions that they find too personal and do not want to share with the interviewer. This information is all discussed with the participant during the informed consent process at the beginning of the study.

18.2 Research team members are trained in interviewing skills, including how to talk with the research participant in an empathic manner that helps put them at ease, which is particularly important considering the sensitive nature of some of the questions. Regarding the TARGET program for those in the treatment groups: all of the interventionist are trained counselors who are trained in working clinically with participants and have experience talking with our research participants in an empathic manner.

18.3 The only information the research team will access that does not come directly from the participants are the administrative data collected from department of corrections databases. This includes the following:

Commented [A3]: Are these all applicable?

- race/ethnicity
- release dates;
- type and length of supervision being released into;
- if you are on court mandated treatment during incarceration or post-release, and what type of treatment is required;
- custody levels at initial assignment and release;
- prison identification number;
- date of birth;
- both community and institutional (at time of entry into facility and final) risk scores, and which assessment tool is used;
- treatment and program participation;
- Protected Health Information from the Department of Corrections database;
- criminal history, including length of sentence, number of priors, age of first arrest, age at present offense, list of convictions, and what you are serving your current sentence on;

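### Protocol 13.1 allows removal from the whole study on an undefined ground, and neither document secures follow-up or as-randomized analysis of the men removed

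*Protocol*

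**What the plan says.** **Removal.** Protocol section 13.0, item 13.1: "The person in charge of the research study or the sponsor can remove you from the research study without your approval". One listed reason is that the man "interfered with ability to complete study protocol". The reasons are given as possible ones, so the list is open. The phrase is not defined, no arm is named, no criteria or independent review are given, and nothing limits its use to the time before randomization.

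**After removal.** Item 13.2 requires a letter giving the reason, and "Subject withdrawals are tracked and reported to the IRB". Item 13.3 says that, for men withdrawn by the team, "the research team will use information collected during the interviews to help determine whether the TARGET model is effective". It is silent on interviews not yet done and on the record search.

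**What each arm is asked to do.** Protocol section 5.0 (items numbered 6.1 and 6.4): "All consented participants (treatment and control) will complete a series of interviews", namely a baseline and three follow-ups (T1 to T3). In addition, "Participants in the comprehensive trauma-based reentry program will participate in up to four group sessions while incarcerated and up to 15 group sessions" after release. Controls have no study sessions.

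**Assurances.** Item 12.1 tells participants that "they can discontinue the study at any point or refuse to answer any questions without consequence". Item 18.1 tells them that "they can choose to stop any interview or intervention session at any time without any consequences or repercussions whatsoever".

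**Analysis.** Recidivism comes from Florida corrections (FDC) and law-enforcement (FDLE) databases for three years (Protocol 6.5). The SAP names no analysis population, makes multiple imputation optional, and censors men without an event at the last time they are known to be event-free. It does not mention removed men.

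**The concern.** Removal here is from the study, not just from the sessions. It is a staff judgement that can be made after assignment, and one arm gives staff far more occasions to make it. The sessions are also group sessions, where one man's conduct can obstruct delivery to others, whereas the interviews are one-on-one.

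Aggression, impulsivity and substance use are mechanisms the trial measures as outcomes. They are also plausible reasons for judging that a man is obstructing the protocol. If removal depends on arm and on such behavior, and outcomes are not collected afterwards, the men left in the two arms are no longer comparable. Covariate adjustment and imputation cannot be relied on to repair this: a man removed before T1 may have only his baseline interview, and the conduct that led to removal is not in the planned models.

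Separately, a man who repeatedly stops sessions is doing what 18.1 says has no consequences. Nothing in 13.1 says whether that could count as interference.

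**Working it through.** **1. Opportunity by arm.** Inputs are from Protocol 5.0.
- Program: 4 + 15 = 19 sessions at most, plus 4 interviews = 23 scheduled contacts.
- Control: 4 interviews.
- Protocol 4.1 also gives up to 14 TARGET sessions (4 + 10). On that count it is 14 + 4 = 18 against 4.
- If the baseline interview precedes assignment, which the documents do not state, the post-assignment counts are 22 against 3.

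The imbalance holds on every count. It is an imbalance of opportunity; the documents give no removal rates.

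**2. The plan's own figures.** The plan states no withdrawal rate, so nothing on this exact point can be reproduced. The nearest figures are the two power statements, used here only as yardsticks.
- Recidivism: medians of 17.28 and 17.28 x 1.39 = 24.02 months, exponential survival, 200 per arm, two-sided 0.05 (sidedness assumed). A fixed 36 months gives 282 events and power 0.790; 18 months' accrual plus 36 months' follow-up gives 311 events and power 0.828. The stated .810 lies between them and is not disputed.
- ANCOVA: 352 men with seven covariates give power 0.80 if .15 is Cohen's f (d = .30), but 0.29 if it is Cohen's d as the SAP states. Both yardsticks are therefore shown below.

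**3. Interview outcomes (assumed inputs).** Let p be the share of program men removed before T1 and delta the number of SDs by which they score worse than the program men who remain. Assume no controls are removed, no true effect and no adjustment. The full-arm mean equals the remaining men's mean shifted by p x delta, so the spurious difference is p x delta. With delta = 0.5:

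| p | Shift (SD) | Share of d = .15 | Share of d = .30 |
|---|---|---|---|
| 5% | 0.05 x 0.5 = 0.025 | 1/6 | 1/12 |
| 10% | 0.10 x 0.5 = 0.05 | 1/3 | 1/6 |
| 20% | 0.20 x 0.5 = 0.10 | 2/3 | 1/3 |

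For scale, the unadjusted standard error with 200 per arm is sqrt(1/200 + 1/200) = 0.10 SD.

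**4. Recidivism (assumed inputs).** Take the SAP's 76.5% three-year risk in both arms with no true effect, and suppose removed program men are dropped entirely, which 13.3 does not say. With share r removed at risk q, the remaining risk is (0.765 - r x q)/(1 - r), and the apparent control-to-program hazard ratio is ln(1 - 0.765)/ln(1 - remaining risk). Example: r = 0.10, q = 0.90 gives (0.765 - 0.09)/0.90 = 0.75, and ln(0.235)/ln(0.25) = 1.045.

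| r | q = 60% | q = 76.5% | q = 90% | q = 100% |
|---|---|---|---|---|
| 5% | 0.975 | 1.00 | 1.02 | 1.04 |
| 10% | 0.95 | 1.00 | 1.05 | 1.08 |
| 15% | 0.92 | 1.00 | 1.07 | 1.13 |

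Values above 1 favor the program. At q = 90%, removing 10% of program men and 5% of controls gives 1.02; removing 10% of both gives 1.00.

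**5. The assurances side by side.** Item 18.1 protects stopping an interview or session, and 12.1 protects discontinuing and declining questions. Item 13.1 permits removal for interference. They collide only if stopping or declining is treated as interference, and the text neither says so nor rules it out.

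**The case against.** The strongest reply is that several harsher readings go beyond the text. That is largely right.

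- A reader might infer that the ground falls almost only on program men. Item 13.1 names no arm, controls can obstruct interviews or tracking, and 19 sessions is a ceiling. What stands is unequal opportunity.
- A reader might infer that 13.1 contradicts 18.1. It does so only if stopping sessions counts as interference. What stands is an unresolved tension.
- A reader might infer that the comparison is biased toward the program as a matter of fact. No document describes who would be removed. The bias vanishes if removals are balanced or removed men are average, and it reverses if they are lower risk.
- A reader might take 13.3 to keep nothing beyond interviews already done, or to end the record search. It says neither. The record search needs no interview, and no section says that removal stops it.
- Withdrawals are tracked with reasons, and baseline interviews are available for ANCOVA or imputation, so the unadjusted shift may overstate the residual bias. True, but tracking documents a removal without recovering the outcome, and imputation is only optional.

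The objection does not dispose of the central gap: an open-ended power of removal, with no statement that follow-up and as-randomized analysis survive its use.

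**Conclusion.** The concern holds as a should-fix. The plan permits team-initiated removal from the whole study on an undefined ground, usable after assignment and with more occasion to arise in the program arm. It does not commit to collecting outcomes afterwards or to analysing all randomized men by assigned arm. That can bias the comparison. Toward the program is the most plausible direction, because conduct likely to be judged as interference overlaps with measured outcomes, but this is a judgement and not something the documents establish.

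Size: 0.025-0.10 SD on interview outcomes for 5-20% of program men removed. This assumes removed men score 0.5 SD worse, no control removals and no adjustment. For recidivism, an assumed 10% removed and dropped entirely gives an apparent hazard ratio between 0.95 and 1.08, according to whether the removed men's risk is 60% or 100%. With no removal rate in either document, these figures show what is possible and are not forecasts. They do not support a must-fix rating.

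**What to change.** 1. Amend 13.1-13.3 so that any team-initiated removal after randomization, on this ground or any other, does not by itself end outcome follow-up. The man stays due for T1-T3 and for the FDC/FDLE record search unless he himself withdraws. Deleting the one phrase would not be enough, because the list of reasons is open.
2. Define the interference ground, and reconcile 13.1 with 12.1 and 18.1 so that a reader can tell whether stopping sessions or declining questions can ever count. Who continues sessions remains the sponsor's decision.
3. Add to the SAP that all randomized men are analysed in their assigned arm, and that removals are reported by arm and reason.

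Cost: a short protocol amendment and a sentence or two in the SAP. The downside is some additional $30 interviews with men who are harder to reach. The change is best made before enrolment, since interview outcomes that were never collected cannot be recovered.

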14.0 Risks to Subjects*

- 14.1* Participants may become emotionally distressed when thinking and talking about the following: their history of participation in crime; history of incarceration; social relationships; services history; behavioral health problems; education attainment; employment status; or transition back to the community. Probability of these risks are low. Our staff is trained to work with participants if they feel emotionally distressed during interviews or service delivery.

All legally available protections will be in place to protect confidentiality of data shared. However, if participants disclose an intent to harm themselves or someone else, this information will be reported to the proper authorities. This procedure will be disclosed in the consent form. However, if people do disclose these intents, it could result in legal or social risks. The same procedure follows if a participant is found to need minor medical or psychological referral, the participant will be encouraged to share this information with research team members. If the medical or psychological need appears to place the participant at risk of harming himself or others, the researcher will immediately share the medical or psychological risk information with the participant's practitioners. The consent form will describe this procedure. If the medical or psychological need appears to place the participant at risk of harming himself or

others, the researcher will immediately contact local authorities about the concern. The consent form will describe this procedure.

Participants may feel distressed by the random assignment process and about the group to which they are randomly assigned. The consent form clearly describes the randomization process and chances of being in the control group, thus the probability of emotional distress is low.

A risk of participation in this study is a breach of confidentiality through the accidental disclosure of the participants' private, identifiable information. Probability of this is low due to use of secure data management systems and constant training with Prison and Research staff on the importance of confidentiality. All interviews are conducted in confidential settings. To minimize risk of accidental disclosure of identifiable private information, a meaningless code number will be established for all participants immediately following consent. That code number will be attached to all interview tools rather than identifying information. A separate document linking identifying information and meaningless ID numbers will be stored apart from consent forms in a locked cabinet in the research team office.

15.0 Potential Benefits to Subjects*

15.1 Possible benefits from the study include discussing the relationships between previous experiences, mental health issues, and criminal offending. The participants may also benefit by thinking about the influence of violence and victimization on your patterns of on patterns of offending, perhaps providing space for you to make difference choices after release. All Participants (Control and Treatment groups)

These participants may benefit from DOC services that include educational and vocational preparation, transition preparedness programming, 12 step groups, behavioral health services, religious programming, and case management.

16.0 Data Management* and Confidentiality

16.1 Data analysis will include statistical techniques such as t-tests, correlations, chi-square testing, ANOVA, survival analysis, structural equation modeling, and multilevel modeling.

16.2 To minimize risk of accidental disclosure of identifiable private information, a meaningless code number will be established for all participants immediately following consent. That code number will be attached to all interview tools rather than identifying information. A separate document linking identifying information and meaningless ID numbers will be stored apart from consent forms in a locked cabinet in the research team office.

16.3 Research team members are all trained on using REDCap to store, encrypt, and protect the data. REDCap servers are housed in a local data center at Florida State University and all web-based information transmission is encrypted. REDCap was developed specifically around HIPPA-Security guidelines. All identifiable information is replaced with a meaningless code number for the sake of confidentiality.

The researchers will obtain the participants department of corrections' identification nm

16.4 Data collectors all have tablets with REDCap. They collect information from the participants on their tablets using REDCap, which is housed in a local data center at FSU. We will maintain all study records, including signed and dated consent documents for six years after completion of the study.

16.5 Data will be stored in REDCap for six years after completion of the study. Research team members have access to the data and are responsible for receipt or transmission of the data..

